6.2 Reporting Procedures

All adverse events are evaluated by [name] and two other Johns Hopkins faculty with respect to intensity, frequency, relationship to study, and outcome.

The protocol for the FEAT trial for reporting AE is the following:

- All AE are recorded on an AE form.
 - a. The AE may be identified from a list of pre-defined complications or from informal review of the electronic medical record by research staff.
 - b. Serious AE will be further recorded on a separate form.
 - c. A panel of three faculty at Johns Hopkins (including [name]) will adjudicate expectedness and relatedness of each AE.
- Serious AE (SAE)
 - a. If **unexpected**, SAE will be reported to the NIA, IRB, and the independent safety officer within 48 hours.
 - b. If **expected**, then SAE will be reported using the SAE form within 14 days of discovery.
 - c. An SAE will be considered expected if it is listed in the DSMP and/or the adjudication committee considers it expected (with consideration that events with <5% incidence should be considered unexpected).
- Non-serious AE that are unexpected, possibly related, and may place participants at greater harm than originally recognized will be reported to the IRB, NIH, and the independent safety officer within 14 days.
- All other adverse events will be maintained in the study database and reported to the IRB during continuing review and to the safety officer every **6 months**.

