6 SAFETY ASSESSMENTS

6.1 Adverse Events and Serious Adverse Events

Adverse events (AE) encountered during or after surgery are recorded on the appropriate AE section of the CRF. Adverse events are defined as any untoward or unfavorable medical occurrence in a human study, including any abnormal sign (for example, abnormal physical exam or laboratory finding), symptom, or disease, temporally associated with the participants' involvement in the research, whether or not considered related to the participant's participation in the research.

Serious adverse events (SAE) are a subset of AE that meet one of the following criteria:

- Results in death
- Is life threatening
- Places the participant at immediate risk of death from the event as it occurred
- Requires or prolongs hospitalization substantially
- Causes persistent or significant disability or incapacity
- Is another condition which investigators judge to represent significant hazards

Severity Classification

Classifications of adverse events include the following:

- **Mild:** Awareness of signs or symptoms, but easily tolerated and are of minor irritant type causing no loss of time from normal activities. Symptoms do not require therapy or a medical evaluation; signs and symptoms are transient.
- **Moderate:** Events introduce a low level of inconvenience or concern to the participant and may interfere with daily activities, but are usually improved by simple therapeutic measures; moderate experiences may cause some interference with functioning
- **Severe:** Events interrupt the participant's normal daily activities and generally require systemic drug therapy or other treatment; they are usually incapacitating

Expectedness of Adverse Events

AEs will be assessed as to whether they were expected to occur or unexpected, meaning not anticipated based on current knowledge found in the protocol, investigator brochure, product insert, or label. Categories are:

- **Unexpected** - nature or severity of the event is not consistent with information about the condition under study or intervention in the protocol, consent form, product brochure, or investigator brochure.
- **Expected** - event is known to be associated with the intervention or condition under study.

Relatedness of Adverse Events

The potential event relationship to the study intervention and/or participation is assessed by the site investigator. A comprehensive scale in common use to categorize an event is:

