- **Definitely Related:** The adverse event is clearly related to the investigational agent/procedure – i.e. an event that follows a reasonable temporal sequence from administration of the study intervention, follows a known or expected response pattern to the suspected intervention, that is

FEAT Study Protocol

confirmed by improvement on stopping and reappearance of the event on repeated exposure and that could not be reasonably explained by the known characteristics of the subject's clinical state.

- **Possibly Related:** An adverse event that follows a reasonable temporal sequence from administration of the study intervention follows a known or expected response pattern to the suspected intervention, but that could readily have been produced by a number of other factors.
- **Not Related:** The adverse event is clearly not related to the investigational agent/procedure - i.e. another cause of the event is most plausible; and/or a clinically plausible temporal sequence is inconsistent with the onset of the event and the study intervention and/or a causal relationship is considered biologically implausible.

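### Read literally, a non-serious harm with no recognised response pattern fits no relatedness category and cannot trigger the 14-day report

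*Combined protocol and SAP*

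**What the plan says.** Section 6.2 (Reporting Procedures) gives faster reporting to "Non-serious AE that are unexpected, possibly related, and may place participants at greater harm than originally recognized". All three conditions must hold. Such events "will be reported to the IRB, NIH, and the independent safety officer within 14 days". For the remainder, the section says: "All other adverse events will be maintained in the study database and reported to the IRB during continuing review and to the safety officer", the latter every 6 months. Serious events have their own rule: an unexpected SAE is reported within 48 hours, and relatedness is not a condition.

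Section 6.1 defines the terms.

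- **Unexpected:** "nature or severity of the event is not consistent with information about the condition under study or intervention in the protocol", or in the consent form or brochures.
- **Expected:** "event is known to be associated with the intervention or condition under study".
- **Possibly Related:** an event with reasonable timing that "follows a known or expected response pattern to the suspected intervention, but that could readily have been produced by a number of other factors".
- **Definitely Related:** among other elements, the event "follows a known or expected response pattern to the suspected intervention, that is" borne out when exposure stops and is repeated.
- **Not Related:** "The adverse event is clearly not related to the investigational agent/procedure - i.e. another cause of the event is most plausible", or the timing does not fit, or causation is biologically implausible.

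A panel of three faculty rates expectedness and relatedness for every adverse event.

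**The concern.** Expectedness and relatedness are meant to be separate judgements: whether this kind of event was foreseen, and whether the intervention may have caused it. Section 6.1 puts part of the first question into the second, because an event counts as related only if its pattern is already known or expected. Section 6.2 then asks for events that are both unexpected and possibly related. The two terms pull against each other, most of all for a harm of a kind not seen before.

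The third condition of the trigger, more harm than had been recognised, shows that this route is meant for emerging signals. If the definitions shut out a harm with no recognised pattern, the route misses one of the events it most plainly exists to catch. Safety is part of the primary goal in section 7.2, and with 25 patients a single unusual event carries weight.

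**Working it through.** There is no figure in the plan to reproduce and no power or sample-size calculation is involved. The check sets the 6.1 definitions against the 6.2 rule.

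**Step 1. Is the pattern a required element?** The Possibly Related sentence runs timing and pattern together without punctuation, so it could be misread. Definitely Related lists the same two items, in the same order, as separate requirements. The natural reading is that both positive categories require the pattern.

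**Step 2. Classify a test event.** Take a non-serious event with reasonable timing, no more plausible cause, a causal link that is not biologically implausible, and no known or expected pattern in any source.

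- Definitely Related: fails on the pattern. It also asks for reappearance on repeated exposure, which is hardly attainable when the intervention is blood-pressure targeting during one operation.
- Possibly Related: fails on the pattern.
- Not Related: none of its three grounds is present.

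The event fits 0 of the 3 categories.

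**Step 3. Apply the trigger.** The event is unexpected by nature, but it is not Possibly Related. The conditions are joined by *and*, so the trigger fails whatever the third condition shows.

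**Step 4. Find the default route.** The event joins the remaining adverse events. Taking a month as 30 days, the safety officer may wait up to 6 × 30 = 180 days instead of 14, a difference of up to 180 − 14 = 166 days. The IRB hears at continuing review, for which no interval is given. The NIH, a recipient on the 14-day route, is not named on the default route.

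**Step 5. See which unexpected events are still caught.**

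| Event | How it is unexpected | Can it be Possibly Related? | Route |
|---|---|---|---|
| Non-serious, known kind, worse than the study information describes | Severity | Yes | 14 days, if the third condition holds |
| Non-serious, absent from the study documents, pattern recognised from another source | Nature | Yes | 14 days, if the third condition holds |
| Non-serious, no recognised pattern in any source | Nature | No | Continuing review and 6-monthly report |
| Unexpected SAE | Either | Not needed | 48 hours |

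Only the third row is misrouted.

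**The case against.** The strongest reply is that the two tests use different yardsticks. Expectedness is judged against named study documents, while the response pattern is not tied to any source. An event missing from those documents but recognisable as a response to vasopressors, fluids or vasodilators can be unexpected in nature and still Possibly Related. This stands. A reader might infer that the two terms exclude each other for every event of unexpected nature, so that only unexpected severity can qualify. The documents do not support that, as the second row of the table shows.

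A reader might also infer that misrouted events would vanish from a tally of related events on which the safety conclusion rests. No such tally is planned. The safety outcomes in section 7.1 are operative bleeding and organ ischemia, with no relatedness condition, and section 7.2 describes no analysis by relatedness.

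Four further points count on the other side.

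- Section 6.1 lets investigators class an event as serious if they judge it a significant hazard. If it is unexpected, it then goes out within 48 hours. This is a real but partial backstop: it works only if the event is upgraded, whereas the 14-day rule is written for events that are not.
- The panel evaluates every event, so the 6-month interval concerns reporting outside the team, not first review. This stands. The panel might also read the terms loosely, but the text gives it no such latitude.
- Section 6.2 asks that events with incidence below 5% be considered unexpected, which suggests that a known but uncommon event can be rated unexpected. That remark sits in the SAE rule, and it does not help an event with no known pattern.
- Such events should be rare in a 25-patient pilot using existing drugs and FDA-approved non-invasive monitors. The documents give no rate, but nothing in them suggests many.

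**Conclusion.** The point holds in a narrow form and is minor. On a literal reading, a non-serious event with plausible timing, no more plausible cause and no recognised pattern in any source has no relatedness category and cannot reach the 14-day route. Its notice to the safety officer may be delayed from 14 days to about 180. The 14-day route is not empty, and unexpected serious events are unaffected.

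This rests on two assumptions: that the pattern is a required element of Possibly Related, as the parallel wording indicates, and that the panel applies the definitions as written. The number of events affected cannot be estimated from the documents and is probably small. It remains worth correcting, because the written rule sends an emerging signal the wrong way; this is more than a missing detail.

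One adjacent gap comes from the same literal reading. The trigger names only possibly related events, so an unexpected, non-serious event rated Definitely Related is also left out.

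**What to change.** 1. In section 6.1, remove the pattern condition from Possibly Related. Define the category as a reasonable temporal sequence with a causal link that is not biologically implausible, even if other factors could have produced the event.
2. Leave the question of whether the event is new to the separate expectedness rating.
3. In section 6.2, word the trigger so that it covers events rated possibly or definitely related.

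The first change gives the uncategorised event a category, and the third closes the adjacent gap. The cost is one sentence in section 6.1 and a few words in section 6.2, with no effect on treatment, outcomes or sample size. A few more non-serious events may go on the 14-day route, but the greater-harm condition stays in place and should keep that number small.

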7. STATISTICAL CONSIDERATIONS

7.1. Outcomes:

Primary outcome variables

Feasibility outcomes will be recruitment >60%, enrollment of at least 3 patients per month, available lower limit of autoregulation target in >65% of all patients, at least 1 delirium assessment in >95%, and at least 1 cognitive and functional assessment in >90%.

Safety outcomes will be increased operative bleeding and significant organ ischemia (myocardial infarction, as judged by treating physicians).

Secondary clinical outcome variables

Extent of mean arterial pressure outside the limits of cerebral autoregulation (after the establishment of the MAP target) will be assessed based on intraoperative monitoring data.

FEAT Study Protocol

Delirium will be assessed in the hospital using the 3D-CAM (CAM-ICU for intubated patients).

Cognitive and functional outcomes will be assessed by telephone at postoperative days 60 and 180, and in-person or by telephone at 1-year follow-up.

- a. Cognitive outcomes are: Short Blessed Test score, Oral Trail Making Test Score, AD8 score
- b. Functional outcomes are: inability to walk ≥ 10 feet without human assistance, WHO-DAS 2.0 score, Instrumental Activities of Daily Living, and institutionalization

7.2. Analytic Plan:

We will examine whether targeting MAP based on the limits of cerebral autoregulation during surgery is feasible and safe, and we will explore whether it can reduce delirium, improve cognition, and improve function. The primary goal is to assess feasibility and safety of the intervention. We will monitor success in implementing each aspect of the protocol, and performance and safety metrics will be compared against pre-specified criteria as defined in the primary outcome section.

We will then assess potential efficacy of the intervention to optimize blood pressure management, reduce delirium, improve SBT score, and improve functional status. The first analysis will be by intention-to-treat by randomization status with primary outcomes of extent of mean arterial pressure outside the limits of autoregulation after establishment of a target, frequency of delirium, change in Short Blessed Test score, and change in WHO-DAS score. We will calculate the mean or frequency of each outcome and between group differences, each with associated 95% confidence intervals. The former will provide estimates of variability in outcomes needed in power calculations for a definitive trial, and the latter will provide a benchmark by which pursuit of a further trial can be evaluated. We will then examine differences in characteristics between groups and in multivariable regression models adjusted for surgery type and age. Finally, we will examine secondary outcomes, including change in OTMT, conversion to dementia, and inability to walk 10-feet. Together, these analyses will inform selection and measurement of primary and secondary outcomes, as well as confounding variables, for a future trial powered for efficacy.

7.3. Sample Size:

Based on the experience of the investigative team, a sample size of 25 patients would allow determination of whether feasibility outcomes had been met and assessment of safety events. Such information would be critically important to support a future trial.

We also calculated a formal sample size to have adequate precision for estimating the primary outcome of delirium. We estimate that a sample size of n=25 would provide the precision to estimate the incidence of delirium to within 16 percentage points using a 95% CI.

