5. STUDY PROCEDURES

5.1. Schedule of Evaluations

Name	HOSPITALIZATION PHASE								FOLLOW-UP PHASE (± 30 days)		
	Screening	Baseline	Day of Surgery	Intraop monitoring	POD 1	POD 2	POD 3	Post Discharge	Day 60	Day 180	Day 365
Demography	✓										
Registration and Contact		✓									
Short Blessed Test		✓									
AD8 (patient or proxy)		✓									
Eligibility Confirmation		✓									
Baseline Exam (Pain scales, OTMT, WHO-DAS 2.0, IADL, BRS, 3D-CAM)		✓									
NIRS Monitoring			✓	✓							
Clearsight or arterial monitoring			✓	✓							
BIS monitoring			✓	✓							
Randomization and Intervention			✓	✓							
Surgery Data Collection									✓		
Postoperative Assessment (3D-CAM, Pain, Adverse Events)					✓	✓	✓				
Discharge Contact Info								✓			
Postoperative Events (Pain, Discharge contact)									✓		
Follow-up (Patient or Proxy) (60, 180, 365 days)									✓	✓	✓
AD8 (Patient or Proxy; 365 days)											✓
Adverse Events			✓		✓	✓	✓	✓	✓	✓	✓
End of Study											✓

¹WHODAS or WHODAS-Proxy to be used as appropriate.

FEAT Study Protocol

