5.2.3 Baseline Data

The following data will be collected onto case report forms (CRFs)

- Participant ID/Screening
- Registration and Contact Information
- Eligibility Confirmation
- Baseline Exam
- Baseline Pain Assessment
- 3D CAM
- Short Blessed Test
- Oral Trail Making Test
- AD8 (patient or proxy)
- WHODAS (or WHODAS Proxy)
- Instrumental Activities of Daily Living
- Brief Resilience Scale

FEAT Study Protocol

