5.2.5 Postoperative Data

The following assessments will be performed and entered in CRFs

Post-op Day #1

- 3D CAM (CAM-ICU for intubated patients)
- Post-op Assessment
- Pain Scales – Post-op
- Adverse Events

Post-op Day #2

- 3D CAM (CAM-ICU for intubated patients)
- Post-op Assessment
- Pain Scales – Post-op
- Adverse Events

Post-op Day #3

- 3D CAM (CAM-ICU for intubated patients)
- Post-op Assessment
- Pain Scales – Post-op
- Adverse Events

Discharge

- Surgery Data Collection
- Postoperative Events
- Adverse Events
- Acute Pain Management
- Discharge Contact Information

Day 60

- Ambulation
- Adverse events
- Pain
- Short Blessed Test
- Oral Trail Making Test
- WHODAS (or WHODAS Proxy)
- Instrumental Activities of Daily Living

FEAT Study Protocol

Day 180

- Ambulation
- Adverse events
- Pain
- Short Blessed Test
- Oral Trail Making Test
- WHODAS (or WHODAS Proxy)
- Instrumental Activities of Daily Living

Day 365

- Ambulation
- Adverse events
- Pain
- Short Blessed Test
- Oral Trail Making Test
- AD8 (patient or proxy)
- WHODAS (or WHODAS Proxy)
- Instrumental Activities of Daily Living

End of Study

- The End of Study form will be filled out at the time the participant completes the study or ends participation early.

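### Optional improvement: section 7.2 analyses SBT, WHO-DAS and OTMT as change scores and leaves the collected baseline score out of every model; adding it is cheap, but the gain may be small or nil

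*Combined protocol and SAP*

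**What the plan says.** Section 7.2 first calculates group means and between-group differences with 95% CIs, by intention to treat. Among the outcomes are "change in Short Blessed Test score, and change in WHO-DAS score". It then turns to "multivariable regression models adjusted for surgery type and age", without saying which outcomes these models cover. OTMT follows: "Finally, we will examine secondary outcomes, including change in OTMT". No model includes a baseline score.

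The baseline scores exist. The schedule in 5.1 lists "Baseline Exam (Pain scales, OTMT, WHO-DAS 2.0, IADL, BRS, 3D-CAM" and has a separate baseline row for the Short Blessed Test (SBT). Section 5.2.3 names SBT, OTMT and WHODAS among the baseline forms. Section 5.2.5 repeats all three at days 60, 180 and 365. Section 7.2 does not say which of these visits defines change.

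Section 7.2 states that feasibility and safety are the primary goal. It also gives the exploratory estimates a use: "The former will provide estimates of variability in outcomes needed in power calculations for a definitive trial". The between-group differences are to be a benchmark for deciding whether to pursue a further trial.

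**The concern.** A change score fixes the coefficient of the baseline score at 1. A model with baseline as a covariate (ANCOVA) estimates it. When the true slope is well below 1, subtracting the whole baseline score adds noise and leaves the comparison exposed to chance differences between the arms at entry. With about 8 controls, such differences can be sizeable.

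What is at stake is limited to the exploratory estimates. As written, the plan yields the SD of change. It does not commit to reporting the baseline SD, follow-up SD, correlation or residual SD, which would be needed to size a definitive trial analysed with baseline adjustment. The documents do not say how that trial will be analysed.

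**Working it through.** **The plan's own figure.** Section 7.3 gives a precision of 16 percentage points for delirium with n = 25. At the 20% incidence mentioned in section 2, 1.96 × sqrt(0.20 × 0.80 / 25) = 0.157, so the figure reproduces. It does not involve these scores and is unaffected.

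**Inputs.** From the documents: 25 patients, 2:1 allocation, two surgical strata, 95% CIs. Assumed: a 17 vs 8 split overall, rho 0.3 to 0.9, k = baseline SD / follow-up SD of 0.7 to 1, normal scores and the same baseline slope in both arms.

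**Large-sample ratio.** In units of the follow-up variance, the change score has variance 1 + k² − 2·rho·k and the ANCOVA residual has variance 1 − rho². The first exceeds the second by (rho − k)². With a common slope, ANCOVA is therefore never less precise in large samples, and the two tie when rho = k. At k = 1 the ratio is (1 + rho)/2, which is 0.65, 0.75, 0.85, 0.90 and 0.95 at rho 0.3, 0.5, 0.7, 0.8 and 0.9.

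**At this sample size.** Example with k = 1, rho = 0.5 and baseline alone added (23 to 22 df): variance ratio 0.75 × (1 + 1/21) = 0.786. The CI width ratio is sqrt(0.786) × 2.074/2.069 = 0.889.

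The table gives simulated mean CI width ratios, ANCOVA (arm, baseline, stratum) over change score (arm only), from 20,000 trials per cell. The 20-patient rows use 13 vs 7 as an assumed loss to follow-up.

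| Patients, k | rho 0.3 | 0.5 | 0.7 | 0.8 | 0.9 |
|---|---|---|---|---|---|
| 25, k = 1 | 0.829 | 0.891 | 0.948 | 0.977 | 1.003 |
| 25, k = 0.8 | 0.911 | 0.973 | 1.019 | 1.028 | 1.004 |
| 25, k = 0.7 | 0.948 | 1.003 | 1.029 | 1.015 | 0.936 |
| 20, k = 1 | 0.842 | 0.905 | 0.963 | 0.992 | 1.018 |
| 20, k = 0.8 | 0.926 | 0.987 | 1.036 | 1.045 | 1.018 |
| 20, k = 0.7 | 0.966 | 1.018 | 1.045 | 1.031 | 0.950 |

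Adding baseline to the planned surgery-type-and-age model gives the same ratios within 0.01.

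**Which k is plausible.** Section 4.1 excludes SBT above 20 and diagnosed dementia, and requires patients to walk at baseline. Follow-up scores have no such limits. A baseline SD smaller than the follow-up SD (k below 1) is therefore plausible for all three scores.

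**Unequal slopes.** Under 2:1 allocation the common-slope result can fail. Assumed illustration: baseline SD 1, slopes 0.5 (intervention) and 1.25 (control), follow-up SDs 1.0 and 1.5.
- Residual variances are 1 − 0.25 = 0.75 and 2.25 − 1.5625 = 0.6875.
- Change score: variances 0.75 + 0.5² = 1.00 and 0.6875 + 0.25² = 0.75, so 1.00/(2/3) + 0.75/(1/3) = 3.75.
- ANCOVA: pooled slope (2/3)(0.5) + (1/3)(1.25) = 0.75, variances 0.75 + 0.25² = 0.8125 and 0.6875 + 0.5² = 0.9375, so 0.8125/(2/3) + 0.9375/(1/3) = 4.031.
- Ratio 4.031/3.75 = 1.075, or 7.5% more variance with ANCOVA.

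**Chance imbalance.** The difference in baseline means has SD sqrt(1/17 + 1/8) = 0.43 baseline SDs. It exceeds 0.5 SD in about 24% of trials (normal approximation). With k = 1, a 0.5 SD imbalance shifts the change-score estimate by (1 − rho) × 0.5 SD: 0.25 SD at rho 0.5 and 0.15 SD at rho 0.7.

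**Planning inputs.** An SD on 23 df has 95% limits of sqrt(23/38.08) = 0.78 and sqrt(23/11.69) = 1.40 times the estimate.

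**The case against.** The planned comparison is valid, and these scores sit in the exploratory tier of a 25-patient pilot. Neither rho nor k is in the documents, so neither the size nor the sign of the gain is established. In the unfavourable cells (k 0.7 to 0.8, rho 0.7 to 0.8, 25 patients), ANCOVA gave the wider interval in 67 to 76% of simulated trials. Section 7.2 sets no numerical threshold on these differences, so no decision is shown to change. The imprecision of any SD at this sample size exceeds most of the possible gain. Individual scores are kept, so the SDs and correlation can be computed later. Covariate choice is also partly something the pilot is meant to inform. Three scores, three visits and two models make 18 adjusted fits in at most 25 patients.

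All of this stands, and it makes the point optional. It does not remove the point. The cost is one or two degrees of freedom. Imbalance at entry is a separate reason to adjust, because stratifying by surgery type does not balance cognition or disability directly. Naming the planning inputs now costs one sentence.

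A reader might infer that the change-score analysis is biased. The documents do not support that, since the arms are randomised. A reader might also infer that baseline adjustment always helps. That fails with unequal slopes under 2:1 allocation and, at this sample size, in several cells with a common slope. Gains of 18 to 27% arise only if baseline scores vary more than follow-up scores (k = 1.25), and nothing in the documents points that way.

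**Conclusion.** This is an optional, inexpensive improvement and not an error. With 17 vs 8 patients, normal scores and a common slope, the CI change runs from 17% narrower to none at k = 1 over rho 0.3 to 0.9. At k = 0.7 to 0.8 it runs from 9% narrower to 3% wider over rho 0.3 to 0.8, and up to about 4.5% wider with 20 patients. Since k below 1 is plausible for all three scores, the precision gain may be small or nil. The firmer reasons to adjust are protection against baseline imbalance and better planning inputs. If the definitive trial were to adjust for baseline, with equal SDs, sizing it from the SD of change alone would overstate its sample size by 1/0.75 − 1 = 33% at rho 0.5 and 1/0.85 − 1 = 18% at rho 0.7. That is conditional on an analysis the documents do not specify. No feasibility or safety criterion changes, and the 16-point delirium precision stands.

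**What to change.** In 7.2, add the baseline score as a covariate, with surgery stratum, to the between-arm comparison of SBT, WHO-DAS and OTMT at each of days 60, 180 and 365. Report each difference with its 95% CI. Add the baseline score to the planned surgery-type-and-age model as well. Either the change or the follow-up score can be the outcome, because the treatment estimate is the same once baseline is in the model. Keep raw means and changes by arm as description. Report the baseline SD, follow-up SD, their correlation and the residual SD as inputs for the definitive trial, and note how imprecise they are.

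The cost is SAP wording and some extra model fits, with no new data. Residual degrees of freedom fall from 23 to 21 in the first comparison and from 21 to 20 in the surgery-type-and-age model (taking surgery type as two categories). In unfavourable cases the interval is slightly wider, as shown above.
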